6.13. Bioanalytical and Pharmacokinetic/Pharmacodynamic Methods

Details of PK/PD analyses can be found in a separate PK/PD analysis plan.

6.14. Safety Analyses

All safety evaluations will be based upon the Safety Population as defined in [Table AMAG.6.1](#).

Safety and tolerability will be evaluated in terms of AEs, clinical laboratory evaluations, vital signs and physical characteristics, safety in special groups and circumstances, including adverse events of special interest (AESI).

Unless otherwise specified, the primary presentations of safety for each of the safety groups will be as follows:

Safety Population Period 1:

Treatment comparisons between all Period 1 LY dose regimens (200 mg IV, 600 mg IV, 1000 mg IV) combined and placebo will be conducted using a Fisher's exact test for select categorical safety outcomes. The p-values are shown to facilitate the review of important safety data and subsequent prioritization and summarization of the data in CSRs. Odds ratios will be created with combined LY as the numerator and placebo as the denominator.

Safety Population Period 2, Safety Population All SC LY, and Safety Population All LY:

Descriptive statistics will be used to identify potential safety signals.

For Safety Population All LY, the following periods (where applicable) will be considered:

- All treatment periods where LY (IV or SC) is administered
- All treatment periods where LY (IV or SC) is administered and Follow-Up

Visualization tools will be used to facilitate the review and understanding of the study-level safety data.

In the event differential dropout rates are seen or to further investigate events of interest, summary tables comparing exposure-adjusted incidence rate (that is, person-time-adjusted incidence rates) may be generated for applicable safety evaluations of interest.

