5.5. Justification for Dose

The dose levels and regimens planned for this study were selected based on analyses of PK, safety, and efficacy data from the single-dose studies AMAA and AMAD, literature information about doses and exposures for other IL-23 antibodies, and nonclinical safety data.

On the basis of simulations conducted using the PK data collected in Study AMAA, a Q4W dosing frequency is not expected to result in any accumulation and the planned doses of 200, 600, and 1000 mg Q4W during the induction period (Period 1) are projected to produce mean trough concentrations of 2.7 to 13 µg/ml. The projected exposures for the planned doses are similar to those that have been evaluated and found to be effective induction regimens in Crohn's disease for the IL-12/IL-23 antibody ustekinumab (Sandborn et al. 2012; Adedokun et al. 2016; and the IL-23 antibody BI-655066 (Feagan et al. 2016).

In Period 2, patients will be randomized to continue their induction regimen or be reduced to a 300 mg SC LY3074828 Q4W regimen. In Period 3, all subjects will be administered 300 mg subcutaneously Q4W. Based on the SC bioavailability of LY3074828, a 300 mg SC dose will produce an exposure area under the plasma concentration versus time curve (AUC) approximately 40% lower and a trough concentration (3.2 µg/ml) that is slightly higher than the lowest induction dose (IV 200 mg). Therefore, data from Period 2 will allow evaluation of response with continued treatment at the induction dose levels versus reduction to a lower exposure level. Experience with anti-tumor necrosis factor (anti-TNF) antibodies in inflammatory bowel disease (IBD) suggests that the exposure required to maintain response in subjects with IBD may be lower than the exposure required to induce response (Rutgeerts et al. 2004).

The margin of safety for the high dose of IV 1000 mg relative to the no-observed-adverse-effect level (NOAEL) observed in the 6-month nonclinical toxicology study in cynomolgus monkeys is 8 based on dose and 1.9 based on AUC (Table AMAG.2). No adverse effects were observed in the 6-month nonclinical toxicology study in cynomolgus monkeys at the highest tested dose (100 mg/kg subcutaneously Q4W).

Table AMAG.2. Margin of Safety for LY3074828 Based on Administered Dose and Predicted Exposure

	Dose (mg/kg)	Dose Multiple^a	AUC_{0-672h,ss} (µg*h/mL)	Margin of Safety^b
Human highest dose (1000 mg IV)^c	12.5 (IV)	8	45600	1.9
Monkey NOAEL^d	100 (SC)		85800 ^e	

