6.1.5. Treatment Groups by Analysis Population and Analysis Period

Table AMAG.6.5 provides the treatment groups to be displayed for each analysis population and analysis period.

Table AMAG.6.5. Treatment Groups by Analysis Population and Analysis Period

Analysis Population	Analysis Period	Treatment Groups	Treatment-Group Comparison, When Applicable
ITT, mITT, Safety Population Period 1	Period 1	
 • PBO • 200 mg IV • 600 mg IV • 1000 mg IV • All LY • Total 	For ITT and mITT: 
 • 200 mg IV vs PBO • 600 mg IV vs PBO • 1000 mg IV vs PBO For Safety Population Period 1: 
 • All LY vs PBO
EHO Group 2, EHO Group 3	Periods 1, 2, 3 and f/u (where applicable)	
 • 200 mg IV/200 mg IV • 600 mg IV/600 mg IV • 1000 mg IV/1000 mg IV • LY IV/300 mg SC • 1000 mg IV for subjects showing no improvement[#] in SES-CD from baseline at Week 12 • Placebo/1000 mg IV • Total 	N/A
Safety Population Period 2	Period 2	
 • 200 mg IV/200 mg IV • 600 mg IV/600 mg IV • 1000 mg IV/1000 mg IV • LY IV/300 mg SC • 1000 mg IV for subjects showing no improvement[#] in SES-CD from baseline at Week 12 • Placebo/1000 mg IV • All LY IV • Total 	N/A
Safety population All SC LY	All treatment periods where LY SC is administered (time during either Periods 2-3)	
 • 300 mg SC * 	N/A
Safety Population All LY	All treatment periods where LY (IV or SC) is administered	
 • LY Treatment * 	N/A

Treatment Groups by Analysis Population and Analysis Period

Analysis Population	Analysis Period	Treatment Groups	Treatment-Group Comparison, When Applicable
Safety Population All LY	All treatment periods where LY (IV or SC) is administered and Follow-Up Period	
 LY Treatment and after * 	N/A

Abbreviations: EHO = efficacy and health outcomes; f/u = follow-up; ITT = intent to treat; IV = intravenous; mITT = modified intent to treat; N/A = not applicable; PBO = placebo; SC = subcutaneous; SES-CD = Simple Endoscopic Score for Crohn's Disease.

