The percentages of subjects with TEAEs will be summarized by treatment using MedDRA PT nested within system organ class (SOC). Statistical comparisons as noted in Section 6.14 will be applied at both the SOC and PT levels. Events will be ordered by decreasing frequency in the total LY treatment group within SOC. These summaries will be presented for Safety Population Period 1, Safety Population Period 2, Safety Population All SC LY, and Safety Population All LY. As an additional table or figure, for Safety Population Period 1, the percentages of subjects with TEAEs will be summarized by treatment using MedDRA PT (without regard to SOC). Events will be ordered by decreasing frequency in the total LY treatment group.

The percentages of subjects with TEAEs by maximum severity will be summarized by treatment using MedDRA PT. For each subject and TEAE, the maximum severity for the MedDRA PT is the maximum postbaseline severity observed from all associated LLTs mapping to the MedDRA PT. Only counts and percentages will be included for the TEAEs by maximum severity. This summary will be presented for Safety Population Period 1, Safety Population Period 2, Safety Population All SC LY, and Safety Population All LY.

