- Outlier/shift displays focusing on low values: A scatter plot, a shift table, and a shift to low table will be created. Unplanned measurements will be included. The scatter plot will plot the minimum value during the baseline period versus the minimum value during the treatment period. The shift table will include the number and percentage of subjects within each baseline category (minimum value is low, normal, high, or missing) versus each postbaseline category (minimum value is low, normal, high, or missing) by treatment. Subjects in the Safety Population will be included in the shift table. The shift from normal/high to low table will include the number and percentage of subjects by treatment whose minimum baseline result is normal or high and whose minimum treatment result is low. Subjects whose minimum baseline result is normal or high and have at least one result during the treatment period are included. The Fisher's exact test will be used to compare percentages of subjects who shift from normal/high to low between all Period 1 LY dose regimens (200 mg IV, 600 mg IV, 1000 mg IV) combined and placebo for Safety Population Period 1.
- Outlier/shift displays focusing on high values: The same approach described for low values will be used, except maximum values will replace minimum values.

Box plots will be displayed for Safety Population Period 1. Spaghetti plots will be explored to evaluate individual subject trends over time across the whole study. The summary of treatment-emergent abnormal, high, or low laboratory results at any time will be provided for Safety Population Period 1, Safety Population Period 2, Safety Population All SC LY, and Safety Population All LY.

For laboratory analyte measurements, a listing of abnormal findings will be created. The listing will include subject ID, treatment group, laboratory collection date, analyte name, and analyte finding.

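### Period 1 safety is tested only as all LY doses combined versus placebo, so its p-values and odds ratios are weak against a dose-related effect, although rates by dose are displayed

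*SAP*

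**What the plan says.** The Safety Population Period 1 text of SAP 6.14 says that treatment comparisons "between all Period 1 LY dose regimens (200 mg IV, 600 mg IV, 1000 mg IV) combined and placebo will be conducted"; the method is Fisher's "exact test for select categorical safety outcomes". The effect measure follows the same split: "Odds ratios will be created with combined LY as the numerator and placebo as the denominator". The same section presents the p-values as an aid to reviewing and prioritising safety data for the study report.

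The contrast carries through the plan. SAP 6.14.2.1 says that the Section 6.14 comparisons "will be applied at both the SOC and PT levels" for adverse events. For laboratory data, SAP 6.14.3 uses Fisher's test to "compare percentages of subjects who shift from normal/high to low between all Period 1 LY dose regimens", again combined, and placebo; high values are handled the same way. Table AMAG.6.5 lists only All LY against placebo for Safety Population Period 1, while the same cell gives ITT and mITT three separate dose-versus-placebo comparisons. Safety after Period 1 is descriptive.

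Display is a different matter. That table "provides the treatment groups to be displayed for each analysis population and analysis period", and for Period 1 it lists placebo, 200, 600 and 1000 mg, All LY and Total. SAP 6.14.2.2 tabulates, for Period 1, every preferred term that reaches 5% in any one treatment group.

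**The concern.** The trial randomises a five-fold dose range, and Period 1 is its only placebo-controlled part. All placebo subjects, and all LY subjects without SES-CD improvement, go to 1000 mg in Period 2. The interim analyses exist to support development planning (Protocol 10.3.7, SAP 6.18), where benefit and risk by dose are natural inputs. Efficacy is tested against placebo dose by dose. Safety is tested only in aggregate.

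Half of the pooled LY group is on the two lower doses. If an adverse effect appears only at, or mainly towards, 1000 mg, the pooled contrast averages it with arms that have little or none of it. The adverse event tables are also ordered by frequency in the total LY group, so both formal aids to prioritisation rest on the pool.

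**Working it through.** **Inputs from the documents.** N = 180, allocated 2:1:1:2 (Protocol 10.1), gives 60 on 1000 mg, 30 on 600 mg, 30 on 200 mg and 60 on placebo. The pooled LY group is 60 + 30 + 30 = 120.

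**The plan's own figures.** The documents give no power for any safety comparison. The efficacy figure confirms the arm sizes: 35% versus 15%, 60 per arm, chi-squared, two-sided 0.1 gives 81.8%, against the stated 81%. The margins in Protocol Table AMAG.2 also reproduce: 85800/45600 = 1.88 (stated 1.9) and 100/12.5 = 8.

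**Assumptions.** The documents give no adverse event rates, and SAP 6.14 sets no p-value threshold for safety. Rates and the 0.05 cut-off below are assumed. Results at 0.10, the general level in Protocol 10.3.1, follow.

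**Dilution.** Pooled rate = (30·p200 + 30·p600 + 60·p1000)/120. With 5% at the lower doses and 20% at 1000 mg: (1.5 + 1.5 + 12)/120 = 12.5%. Against 5% on placebo, a 15-point excess becomes 7.5 points. The larger group does not make up for this: √(1/120 + 1/60) = 0.158 against √(1/60 + 1/60) = 0.183, so the standard error falls by about 13% (at equal variance) while the difference falls by 50%.

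**Chance of a flag.** For Fisher's test, the binomial probabilities of all outcomes with p ≤ 0.05 are summed (120 v 60 and 60 v 60). The trend test is the asymptotic Cochran-Armitage, simulated: Z = Σx(d − d̄)/√[p̄(1 − p̄)Σn(d − d̄)²], with d = 0, 200, 600, 1000 and d̄ = 84000/180 = 466.7.

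| Assumed rates, placebo/200/600/1000 mg | Pooled Fisher | 1000 mg v placebo Fisher | Trend |
|---|---|---|---|
| 5/5/5/20% | 28% | 63% | 80% |
| 2/2/2/15% | 30% | 64% | 86% |
| 5/7/12/20% (graded) | 44% | 63% | 78% |
| 5/20/20/20% (all doses) | 79% | 63% | 54% |
| 5/5/5/5% (no effect) | 3% | 1% | 5% |

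The 63% repeats because those rows share the same placebo and 1000 mg rates. At 0.10 the first row becomes 43%, 76% and 87%; with the effect at all doses, pooled gives 89% and 1000 mg alone 76%. The ordering does not depend on the cut-off.

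**Flag on either the pooled or the trend test, at 0.05.** About 80% for 5/5/5/20%, 83% for 5/20/20/20%, and 7% with no effect.

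**One illustrative result.** Events 3/60, 1/30, 2/30 and 12/60. Pooled 15/120 v 3/60: odds ratio (15×57)/(105×3) = 2.7, p = 0.19. 1000 mg v placebo: odds ratio (12×57)/(48×3) = 4.75, p = 0.025. Trend: Z = 5000/1718 = 2.91.

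**The case against.** The case for the plan is substantial, and most of it stands.

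- **Rates by dose will be seen.** Adverse events, serious events and discontinuations are summarised by treatment, with a column per dose. The common-event rule works per arm: at a true 15% or 20% on 1000 mg, at least 3 of 60 subjects (5%) have the event in over 99% of trials, so a preferred term of that size enters the table whatever the pooled p-value. A reader might infer that a top-dose toxicity would go unnoticed; the documents do not support that. The common-event rule does not, however, cover laboratory shifts.
- **The p-values decide nothing.** They aid review, and no dose-selection rule uses them. That a dose would be carried forward because of them is conjecture.
- **Pooling is sometimes better.** It wins clearly when all doses share the effect, and two arms of 30 say little alone. This supports keeping it; it does not argue against adding to it.
- **The safety margin is not a warning.** Protocol 5.5 begins "The margin of safety for the high dose of IV 1000 mg relative to the no-observed-adverse-effect level" and gives 1.9 on AUC. A reader might take this as a sign of expected toxicity at 1000 mg. The same paragraph says that no adverse effects were seen at the highest animal dose tested, so 1.9 is a ratio to the highest exposure studied, not to a toxic one.
- **Further comparisons are allowed.** Protocol 10.3.4 permits more analyses between treatment groups but names none. The exposure-response models in Protocol 10.3.5 are described for SES-CD and CDAI. The separate PK/PD plan is not available here. A contrast chosen after unblinding is weaker than one written beforehand.

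**Conclusion.** The point holds as a minor one. The only specified Period 1 safety tests and odds ratios combine the three doses, and neither document specifies a dose contrast or trend for safety. If an excess is confined to 1000 mg, the pooled difference is half the true one, and the chance of a p-value below 0.05 is about 28%, against 63% for the direct comparison and 80% for a trend test. The planned test also trails when the effect is graded by dose (44%, against 63% and 78%).

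The arm sizes come from the protocol; the event rates and cut-off are assumptions. The result concerns tests and odds ratios only: descriptive safety by dose is planned. It is no evidence of harm at any dose and no reason to drop the pooled contrast.

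**What to change.** In SAP 6.14, 6.14.3 and the Safety Population Period 1 row of Table AMAG.6.5, keep All LY versus placebo. For the same categorical outcomes add, labelled supportive and unadjusted:

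1. an exact Cochran-Armitage trend test with scores 0/200/600/1000 mg;
2. the odds ratio for 1000 mg versus placebo, with its confidence interval.

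State that the trend result is read alongside the pooled one when signals are prioritised.

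The cost is SAP wording and extra table columns, with no new data and no change in sample size. The screen would raise a few more chance flags, about 7% per outcome on pooled or trend against 3% for pooled alone (5% in every arm, p<0.05). The exact trend test should give up only about one point of the power shown for the asymptotic version.

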6.14.1. Extent of Exposure

Duration of exposure to study treatment will be summarized by treatment group for Safety Population Period 1, Safety Population Period 2, Safety Population All SC LY, and Safety Population All LY. For each of the Safety Populations, exposure will be calculated as the period defined in [Table AMAG.6.4](#) plus 1 day.

Total patient-years of exposure will be reported for each of the Safety Populations by treatment (where applicable). Descriptive statistics (n, mean, SD, minimum, first quartile, median, third quartile, and maximum) will be provided for patient-days of exposure and the frequency of subjects falling into the following different exposure ranges, as appropriate, will be summarized:

- >0, ≥7 days, ≥14 days, ≥30 days, ≥60 days, ≥90 days, ≥120 days, ≥183 days, ≥365 days, ≥548 days, and ≥730 days.
- >0 to < 7 days, ≥7 to <14 days, ≥14 to <30 days, ≥30 to < 60 days, ≥60 to <90 days, ≥90 to <120 days, ≥120 to <183 days, ≥183 to <365 days, ≥365 days to <548 days, ≥548 days to <730 days, and ≥730 days.

Overall exposure will be summarized in total patient-years, derived in the following manner:

- Exposure in patient-years = Sum of duration of exposure in days (for all subjects in treatment group) / 365.25.

Additional exposure ranges may be considered if necessary.

No p-values will be reported in these tables as they are intended to describe the characteristics of the Safety Populations.

Reasons for not taking planned treatment and reasons for IV interruptions will be reviewed.

6.14.2. Adverse Events

6.14.2.1. Analysis of Adverse Events (AEs)

A TEAE is defined as an event that first occurred or worsened in severity after baseline. Both the date/time of the event and the date/time of the dose are considered when determining TEAEs. TEAEs will be assigned to the study period(s) (see [Table AMAG.6.4](#)) to which they are considered treatment-emergent:

- For each Medical Dictionary for Regulatory Activities (MedDRA) PT, treatment-emergence will be determined based on whether the PT first occurred during the treatment period or whether any lowest level term (LLT) associated with the PT increased in severity relative to baseline.

- The maximum severity recorded for each LLT prior to the first dose date/time in the period will be used as the pre-treatment severity for that LLT. If an event during the baseline period has missing severity, and the event persists during the treatment period, then it will be considered as treatment-emergent, regardless of the postbaseline level of severity. Events with a missing severity during the treatment period will be considered treatment-emergent.
- Adverse events with a particular LLT will be classified as treatment-emergent if they first start on or after the first dose date/time in the treatment period (that is, a subject has no preexisting conditions with that LLT), or if the severity is greater than the pre-treatment severity for that LLT. If a partial AE start date/time is present, the date/time will be compared as far as possible to the treatment start date/time in order to determine whether the event is treatment-emergent or not. If there is any doubt, the event will be flagged as treatment-emergent.

In an overview table, the number and percentage of subjects who experienced a TEAE, serious adverse event (SAE), died due to an AE, or discontinued from study treatment due to an AE will be summarized by treatment. These summaries will be presented for Safety Population Period 1, Safety Population Period 2, Safety Population All SC LY, and Safety Population All LY. Note that for events that are gender-specific, the denominator and computation of the percentage will include only subjects from the given gender.

The percentages of subjects with TEAEs will be summarized by treatment using MedDRA PT nested within system organ class (SOC). Statistical comparisons as noted in Section 6.14 will be applied at both the SOC and PT levels. Events will be ordered by decreasing frequency in the total LY treatment group within SOC. These summaries will be presented for Safety Population Period 1, Safety Population Period 2, Safety Population All SC LY, and Safety Population All LY. As an additional table or figure, for Safety Population Period 1, the percentages of subjects with TEAEs will be summarized by treatment using MedDRA PT (without regard to SOC). Events will be ordered by decreasing frequency in the total LY treatment group.

The percentages of subjects with TEAEs by maximum severity will be summarized by treatment using MedDRA PT. For each subject and TEAE, the maximum severity for the MedDRA PT is the maximum postbaseline severity observed from all associated LLTs mapping to the MedDRA PT. Only counts and percentages will be included for the TEAEs by maximum severity. This summary will be presented for Safety Population Period 1, Safety Population Period 2, Safety Population All SC LY, and Safety Population All LY.

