Safety Population Period 2 [Weeks 12-52]	2.1) Treatment-Emergent Adverse Events	An event ongoing at the time of the first dose of Period 2 study treatment. If time is not collected for an event starting on Visit 8 dose date, it will be assumed that it occurred after first dose.	Period 2 (Weeks 12-52): starts at Period 2 Start Date and ends at Period 2 End Date or the day of the study treatment disposition visit (whichever is earliest) unless otherwise noted.
	2.2) Treatment-Emergent Abnormal Labs and Vital Signs	The last non-missing assessment (scheduled or unscheduled) recorded prior to the first dose of Period 2 study treatment. If time is not collected for a measurement taken on Visit 8 dose date, it will be assumed that it occurred prior to first dose.	Period 2 will be defined as above (2.1). All scheduled and unscheduled measurements will be included.
	2.3) Change from Last Baseline to Week xx and to Last Postbaseline for Labs and Vital Signs	The last non-missing scheduled assessment recorded prior to the first dose of Period 2 study treatment. If time is not collected for a measurement taken on Visit 8 dose date, it will be assumed that it occurred prior to first dose.	Period 2 will be defined as above (2.1). Only scheduled visits will be included. The ETVs are considered scheduled visits.
Safety population All SC LY [All treatment periods where LY SC is administered]	3.1) Treatment-Emergent Adverse Events	An ongoing event at the time of the first dose of LY SC treatment. If time is not collected for an event starting on the first dose date, it will be assumed that it occurred after first dose.	LY SC Treatment Period: starts at the administration of the first dose of LY SC treatment and ends at the study treatment disposition visit (ie, the last visit at which the LY SC treatment was administered).
	3.2) Treatment-Emergent Abnormal Labs and Vital Signs	The last non-missing assessment (scheduled or unscheduled) recorded prior to the first dose of LY SC treatment. If time is not collected for a measurement taken on first dose date, it will be assumed that it occurred prior to first dose.	LY SC Treatment Period will be defined as above (3.1). All scheduled and unscheduled measurements will be included.

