	3.3) Change from Last Baseline to Week xx and to Last Postbaseline for Labs and Vital Signs	The last non-missing scheduled assessment recorded prior to the first dose of LY SC. If time is not collected for a measurement taken on first dose date, it will be assumed that it occurred prior to first dose.	LY SC Treatment Period will be defined as above (3.1). Only scheduled visits will be included. The ETVs are considered scheduled visits.

Baseline and Postbaseline Definitions for Safety Analyses

Safety Group	Analysis Type	Baseline (Periods as defined in Table AMAG.6.2)	Postbaseline (Periods as defined in Table AMAG.6.2)
Safety Population All LY (a) [All treatment periods where LY (IV or SC) is administered]	4a.1) Treatment-Emergent Adverse Events	
Randomized to LY at Period 1: The baseline period is defined as the Study Baseline period. If time is not collected for an event starting on Visit 2 dose date, it will be assumed that it occurred after first dose.
 
Randomized to Placebo at Period 1: An ongoing event at the time of the first dose of Period 2 study treatment of LY. If time is not collected for an event starting on Visit 8 dose date, it will be assumed that it occurred after first dose.
	
Randomized to LY at Period 1: LY Treatment Period: starts at Period 1 Start Date and ends at the study treatment disposition visit (ie, the last visit at which the LY treatment was administered).
 
Randomized to Placebo at Period 1: LY Treatment Period: starts at the administration of the first dose of Period 2 study treatment of LY and ends at the study treatment disposition visit (ie, the last visit at which the LY treatment was administered).

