6.14.8.2. Infections

Infections will be defined using the PTs from the MedDRA Infections and Infestations SOC.

Treatment-emergent infections will be analyzed according to various groups of infectious events including:

- all infections
 - all PTs in the Infections and Infestations SOC by maximum severity,
- serious infections
 - all PTs in the Infections and Infestations SOC that are SAEs,
- Opportunistic infections (OIs), as described below.

The MedDRA terms used to identify infections typically considered to be potential OIs are based on Winthrop et al. (2015) and are listed in [Appendix 7](#). The list contains relevant groupings of PTs, that is, narrow search terms and broad search terms, which together can assist in identifying subjects of interest. The list of terms is currently based on MedDRA version 19.1, but the list will be updated with each new version of MedDRA, including versions released after finalization of the statistical analysis plans but before database lock. For each of all infections and serious infections, the number and percentage of subjects overall and for each specific PT will be summarized by treatment, with specific event terms ordered by decreasing frequency in the total LY treatment group.

The number and percentage of subjects with TEAEs that are considered as OIs will be summarized by using PT nested within categories. For these TEAEs, the summary table will pool the narrow and broad terms together. Events will be ordered by decreasing frequency in the total LY treatment group.

These summaries will be presented for Safety Population Period 1, Safety Population Period 2, Safety Population All SC LY, and Safety Population All LY.

Visual techniques will be used to examine subjects experiencing treatment-emergent infectious AEs in the context of subject demographics, treatment group, treatment start and stop dates, infectious event, event start and stop dates, event severity and possible relationship to the study drug, total leukocytes, total lymphocytes, absolute neutrophils, event seriousness, event outcome, whether the subject was immunized for tuberculosis and/or herpes zoster, infecting agent, infection site, and whether anti-microbial treatment was recorded.

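### SAP Table AMAG.6.4 and SAP 6.14.2.1 use different adverse event baselines for Period 2, SC dosing and former placebo subjects, so some recurrences count under one and not the other

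*SAP*

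**What the plan says.** SAP 6.1.4, Table AMAG.6.4, sets the treatment-emergent adverse event (TEAE) baseline by population:

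- Safety Population Period 2 (row 2.1): "An event ongoing at the time of the first dose of Period 2 study treatment".
- Safety Population All SC LY (row 3.1): "An ongoing event at the time of the first dose of LY SC treatment".
- Safety Population All LY, randomized to placebo in Period 1 (rows 4a.1 and 4b.1): "An ongoing event at the time of the first dose of Period 2 study treatment of LY".
- Safety Population Period 1 (row 1.1), and All LY for subjects randomized to LY: "The baseline period is defined as the Study Baseline period".

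SAP 6.14.2.1 refers to that table for assigning TEAEs to periods, then gives its own rules:

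- Severity: "The maximum severity recorded for each LLT prior to the first dose date/time in the period will be used as the pre-treatment severity".
- Preferred term (PT): "treatment-emergence will be determined based on whether the PT first occurred during the treatment period", or whether a lowest level term (LLT) under it became more severe.
- LLT: an event qualifies if it starts on or after first dose, glossed as "that is, a subject has no preexisting conditions with that LLT), or if the severity is greater than the pre-treatment severity for that LLT".

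SAP 6.14.8.2 builds on this status: "Treatment-emergent infections will be analyzed according to various groups of infectious events including" all infections, serious infections and opportunistic infections. The hypersensitivity analyses in SAP 6.14.8.3 also use TEAEs. Both sets are produced for Period 1, Period 2, All SC LY and All LY.

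**The concern.** The table asks whether an earlier event is still ongoing at first dose. Section 6.14.2.1 asks only whether the term was recorded earlier, and how severely. For Period 1 the two agree, because everything recorded before the first dose lies in the Study Baseline period. They part in the later populations, where the time before first dose includes weeks on study treatment. For most subjects in Period 2 and All SC LY that treatment was LY itself, so an event on earlier LY could remove its own recurrence from the table.

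This matters because Period 2 is the only safety display of maintenance by regimen, and All SC LY is the only one that pools all SC exposure. SAP Table AMAG.6.5 shows All LY as a single column. Two programmers following different sections would produce different counts.

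**Working it through.** The plan states no figure on this point, so there is none to reproduce. The check applies both rules to the same event histories and then looks at the look-back each implies.

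**Step 1. Both rules on 12 histories (one LLT).** Under Table AMAG.6.4, an earlier event sets the comparison severity only if it is ongoing. Under 6.14.2.1, read literally, any earlier record sets it. An event is treatment-emergent if it exceeds that severity.

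| Earlier event | New event | Table AMAG.6.4 | SAP 6.14.2.1 |
|---|---|---|---|
| None | Mild, moderate or severe | TEAE | TEAE |
| Resolved, mild | Mild | TEAE | **Not** |
| Resolved, mild | Moderate or severe | TEAE | TEAE |
| Resolved, moderate | Mild | TEAE | **Not** |
| Resolved, moderate | Moderate | TEAE | **Not** |
| Resolved, moderate | Severe | TEAE | TEAE |
| Ongoing, mild | Mild | Not | Not |
| Ongoing, mild | Moderate or severe | TEAE | TEAE |

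The table counts 11 of 12 histories and 6.14.2.1 counts 8. All 3 disagreements are recurrences, after resolution, at equal or lower severity. For example, mild nasopharyngitis at Week 3 that resolves and returns, again mild, at Week 30 is a Period 2 TEAE under the table and not under 6.14.2.1.

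**Step 2. Look-back under 6.14.2.1.** Screening lasts up to 28 days (4 weeks) and Period 1 lasts 12 weeks (SAP section 5).

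- Period 2, or SC started at Week 12: 4 + 12 = about 16 weeks.
- SC started at Week 52, after IV treatment in Period 2: 4 + 52 = about 56 weeks.

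All SC LY pools both kinds of SC starter, so its members would be screened against unequal histories. The table's ongoing-event rule has no such imbalance.

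**Step 3. Illustration of size (assumed rates).** Assume a constant, independent rate r per subject-year for one LLT, with every episode resolving and of equal severity. Among subjects with an event in the period, the share not counted is the chance of at least one earlier episode in w weeks:

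share = 1 − exp(−r × w/52)

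For r = 0.5: at w = 16, 1 − exp(−0.154) = 14%; at w = 56, 1 − exp(−0.538) = 42%.

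| Assumed r | 16 weeks | 56 weeks |
|---|---|---|
| 0.1 | 3% | 10% |
| 0.2 | 6% | 19% |
| 0.5 | 14% | 42% |
| 1.0 | 27% | 66% |

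None of these rates is in the documents. The table shows only how the effect grows with event frequency and look-back.

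**The case against.** The strongest reply is that the sections can be read together. Section 6.14.2.1 defines a TEAE relative to baseline and points to Table AMAG.6.4, so the table could say which events are baseline and the bullets only how severity is compared. A resolved Period 1 episode need not be a preexisting condition, and its recurrence has a new start date. That reading is possible and would remove the conflict, but the SAP does not state it. The severity bullet carries its own look-back, and the PT bullet reinforces it. The instruction to flag doubtful events as treatment-emergent follows the partial-date rule and does not clearly reach resolved events.

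SAP 6.1.4 also says that an alternative safety baseline may be considered after the first interim lock. Its example uses screening as the Period 2 baseline for subjects on LY in Period 1. That would not let a resolved Period 1 event mask a recurrence either, but it is optional and does not settle which rule applies now.

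Three limits stand in full:

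- A reader might infer that recurrent events disappear from the long-term safety record. The documents do not support that. All LY uses Study Baseline for subjects randomized to LY, so an event first arising in Period 1 is counted there.
- A reader might infer that serious recurrences are hidden. The SAE and AE-discontinuation summaries in SAP 6.14.2.3 are not worded as TEAE-only, and the site-reaction summaries in SAP 6.14.8.4 use reported events.
- Period 2, All SC LY and All LY are descriptive, so no test depends on the rule.

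**Conclusion.** The SAP holds two stated rules that give different counts for one defined kind of event: a recurrence under the same LLT, after resolution, at equal or lower severity. The affected outputs are the TEAE, infection and hypersensitivity tables for Period 2 and All SC LY, and those for All LY as far as former placebo subjects are concerned. More severe recurrences and the Period 1 tables are unaffected.

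This rests on reading 6.14.2.1 literally. The size cannot be stated, because the documents give neither event rates nor recurrence rates, and a specific number of percentage points would be only the product of assumptions. It is a minor point of specification, worth settling because the two rules cannot both be programmed.

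**What to change.** In SAP 6.14.2.1, state that both pre-treatment severity and preexisting status are taken only from events in the Table AMAG.6.4 baseline for the population analysed. For Period 2, All SC LY and former placebo subjects in All LY, these are events ongoing at the first dose of that treatment.

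Reword the PT and LLT bullets to match. Changing the severity bullet alone would leave both able to exclude a recurrence. Keep the current rule for Period 1, and make any alternative baseline adopted under SAP 6.1.4 apply to both sections.

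The cost is a few sentences, a small programming change and slightly higher TEAE counts in the affected tables. No new data are needed.
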